### III: Population and sampling

#### 3.0: Study unit

The study unit is the participant.

#### 3.1: Reference population

Men and women above the age of 55 years.

#### 3.2: Study population

##### 3.2.1: Inclusion criteria.

Osteopeni patients (OP) of both genders above 55 years of age. OPs are defined as patients with T-score below 0.0 but larger than -2.5.

##### 3.2.2: Exclusion criteria.

Men and women who fulfils at least one of the following criteria will be excluded from participation in the study:

- Eating disorder
- Known gastrointestinal disorder.
- Abnormal liver or kidney function.
- Diabetes mellitus type I.
- Diabetes type II without sufficient control.
- Suffering from verified cancer.
- Under systemic treatment with corticosteroids or other immunosuppressive drugs the last 3 weeks before start of the trial treatment.
- Under active antiresorptive treatment or anabolic treatment.
- Participating in another clinical trial with pharmaceuticals the last six weeks before start of this trial treatment.
- Known milk product allergy.
- Not able to understand information.
- Do not want or not able to give written consent to participate in the study.

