### 1.6.2 Randomization:

Patients included in the study will be allocated to one of the two treatment groups by block randomization with random block size between 2 and 6.

**1.7: Main variables:** The main response variable will be the change in Bone Mineral Density (BMD) and recorded at baseline and every 16 weeks. The second main variables will be total Osteocalcin (tOC), carboxylated osteocalcin (cOC), the osteocalcin ratio  $R_O$  defined as the ratio between cOC and under-carboxylated osteocalcin (ucOC) [ $R_O = cOC / ucOC$ ] and measured at start, week 4, week 16, week 20, week 32 and week 48. Additionally, the bone markers cross-linked C-telopeptide type I collagen (CTX), procollagen type 1 N-terminal propeptide (PINP), bone specific ALP (BALB) and Parathyroid hormone (PTH) will be measured at the same visits. At baseline and every 16 weeks, the following variables will be measured: Vitamin K2 and the different vitamers MK-7, MK-8, MK-9, and MK-9(4H) used as explanatory variable; Diet registration as controlling variables and HbA1C, Lipids, biochemical variables together with “Quality-of-Life” (QoL) questionnaire as supporting variables. The Interleukins IL-1 $\beta$ , IL6, IL8, IL10 and the Cytokines TNF- $\alpha$ , NF- $\kappa$ B (RANK-L), OPG and TGF- $\beta$  will be measured initially and at the last visit in the study. The Common Terminology Criteria for Adverse Events version 4.0 (CTCAE) will be used for registration of Adverse Events (AE) and toxicity score at every investigation visit.

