### 2.2: Osteocalcin and Vitamin K

Activated osteocalcin has a key role in bone formation and maintenance. It is one of the body's 17 so called GLA proteins, all of which being activated by carboxylation in a process involving vitamin K. While vitamin K dependent coagulation factors are practically fully carboxylated under normal conditions, osteocalcin is not. The ratio of fully carboxylated to under carboxylated osteocalcin in the blood (OR) reflects a person's vitamin K status. The high levels of under carboxylated osteocalcin in healthy people indicate that suboptimal vitamin K status or subclinical vitamin K deficiency is common in Western societies. Very low ORs have been associated with osteoporotic fractures.

Figure 1 shows the structure of common forms of vitamin K. Vitamin K1 is produced in plants and found at high concentrations in leafy vegetables and is the dominating variant in the Western diet.

[figure not shown]

Figure 1: Structures of some vitamin K variants

Vitamin K2 (menaquinone, MK) is found in several variants (Fig 1). The short-chained MK-4 can be formed from vitamin K1 in humans and is found in animal products like liver. The K2 vitamers with longer side chains, like MK-7, MK-8, MK-9 and MK-9(4H) are of bacterial origin. They can be found in certain fermented foods. In the Western diet fermented dairy products like cheese are the main source of vitamin K2.

The long chained MKs have been found to have greater extra-hepatic activity than K1 and MK-4, possibly due to more efficient uptake and much longer serum half-life. Prospective cohort studies have demonstrated health benefits that can be attributed the intake of vitamin K2 but not K1, and the main contributor to the vitamin K2 is cheese containing MKs with long side chains.

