## VII. Consideration

### 8.1: Consideration of steering committee

The study will be carried out according to the Helsinki declaration with latest amendments, Good Clinical Practice (GCP) and International Ethical Guidelines for Health-related Research Involving Humans (CIOMS guidelines). The participants are risk patient for Osteoporosis and will only be included in this clinical trial after approval of the trial by the regional Ethical Committee (REK) and the patients have received oral and written information and signed informed consent.

The product to be used in this trial is Jarlsberg cheese commercially available in Norway. To the best of our knowledge, no AE is reported except from person with intolerance of milk and milk product. It is known that vitamin K2 passing a certain daily dose may increase and strengthen the bone density and may therefore have a prophylactic effect on bone fracture. Jarlsberg cheese is shown to be one of the Norwegian produced cheeses with the highest level of vitamin K2.

In a previously conducted dose-response study on healthy fertile women we found the optimal efficacy dose (OED) to increase the osteocalcin levels. Our hypothesis is that this effect is caused by the fermentation of lactic acid to propionic acid by the *Propionibacterium freudenreichii* in the Jarlsberg Cheese, producing MK 9-4H K2 vitamer and DHNA. The first aim of this study is to compare the effects with the commonly used prophylactic treatment of vitamin D + calcium to verify the hypothesis. Our second aim is to study the development of BTM and BMD by the OED of Jarlsberg Cheese and to verify if the cheese could be recommended as prophylactical treatment to osteoporosis.

All participants invited to this clinical trial are entitled to make their decision based on the fullest amount of information available at that time. To make the choice, they will be given a written document expressed in a clear concise language of their native tongue to consider. The document will tell potential participants about the aim of the study. Additionally, that blood sampling will be performed between five and seven times in connection with clinical examinations during the two study parts.

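### Section 3.2.2 does not exclude users of vitamin K antagonists, in whom cOC and R_O would be harder to read as vitamin K status

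*Protocol*

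**What the plan says.** Section 3.2.1 admits "Osteopeni patients (OP) of both genders above 55 years of age" within a T-score range and sets no condition on medication. Section 3.2.2 then lists twelve exclusions under the sentence "Men and women who fulfils at least one of the following criteria will be excluded from participation in the study". Two of them concern drugs that disturb bone outcomes: "Under systemic treatment with corticosteroids or other immunosuppressive drugs the last 3 weeks before start of the trial treatment" and "Under active antiresorptive treatment or anabolic treatment". A third bars recent participation in another drug trial. Anticoagulants and clotting disorders are not mentioned.

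Section 2.2 gives the biological rationale. Osteocalcin is one of a family of proteins, "all of which being activated by carboxylation in a process involving vitamin K". The next comparison brings in coagulation: "While vitamin K dependent coagulation factors are practically fully carboxylated under normal conditions, osteocalcin is not". The same section takes the ratio of carboxylated to under-carboxylated osteocalcin as a reflection of a person's vitamin K status.

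On outcomes, section 1.7 states "The second main variables will be total Osteocalcin (tOC), carboxylated osteocalcin (cOC), the osteocalcin ratio", with R_O defined as cOC divided by ucOC. The main response variable is the change in BMD.

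On risk, section 8.1 reports that, to the authors' knowledge, "no AE is reported except from person with intolerance of milk and milk product".

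**The concern.** The exclusion list already follows the principle that drugs which disturb the bone measurements should not be present at entry. A vitamin K antagonist fits that principle for the osteocalcin outcomes. As the class name says, it opposes the vitamin whose action cOC and R_O are meant to show. A site that applies 3.2.2 as written would have no ground to turn such a patient away.

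Two things are at stake. First, in a user R_O no longer has the plain meaning that section 2.2 gives it, because the drug as well as vitamin K status would influence it. Second, the protocol itself names the coagulation factors as dependent on vitamin K and supplies a food selected for its vitamin K2, yet its risk statement in 8.1 does not mention coagulation.

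**Working it through.** **1. Is the gap closed elsewhere?** The protocol has no list of prohibited medication.

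| Place in the protocol | What it does |
|---|---|
| 3.2.1 | Age and T-score only |
| 3.2.2 | Twelve items, none covering anticoagulants |
| 1.11, 6.2.2, 6.2.3 | Concomitant medication is recorded, not restricted |
| 1.11, 5.4.1, 5.4.2 | No clotting test among the blood samples |
| 6.4 | Cheese stops only after a life-threatening or serious event |
| 8.1 | Names milk intolerance only |

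The exclusions for liver, kidney and gastrointestinal conditions do not cover a patient who simply takes an anticoagulant.

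**2. Does the protocol's own reasoning make the gap matter?** Section 2.2 says that osteocalcin is carboxylated with the help of vitamin K and that R_O reflects vitamin K status. Sections 2.3 and 8.1 say the cheese is rich in K2. Section 1.7 makes cOC and R_O second main variables, and ucOC is the denominator of R_O. The one step not written down is that a vitamin K antagonist works against vitamin K. That is taken from the class name and is an assumption here.

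**3. Who is exposed?** Both arms. The Jarlsberg arm eats the cheese from baseline and, under section 4.1, controls switch to it at week 16 for 32 weeks.

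**4. How many users might enrol?** The protocol gives no prevalence, so q is an assumption. With 30 per group (1.9), 60 patients are included. The expected number is 60 × q, and the chance of at least one is 1 − (1 − q)^60.

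| Assumed q | Expected users | Chance of at least one |
|---|---|---|
| 1% | 0.6 | 45% |
| 2% | 1.2 | 70% |
| 3% | 1.8 | 84% |
| 5% | 3.0 | 95% |

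**5. What could that do to an osteocalcin comparison?** This is an illustration only. Assume a true effect of 1 SD (borrowed from the BMD sample size), 24 completers per group, an unchanged SD, and k users in the Jarlsberg arm who do not respond at all. The average effect falls to (1 − k/24) SD, and power is approximately Φ[(1 − k/24) × √(24/2) − 1.96].

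- k = 0: Φ(3.464 − 1.96) = 93.4%. For the same 24 patients the protocol states 90% in 1.9 and 95% in 11.3; that discrepancy is a separate matter.
- k = 1: Φ(3.320 − 1.96) = 91.3%
- k = 2: Φ(3.175 − 1.96) = 88.8%
- k = 3: Φ(3.031 − 1.96) = 85.8%

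**6. Would the arms differ systematically?** No. Randomisation spreads users evenly on average. Chance imbalance remains possible: if three users enrol, all three fall in the same arm with probability about 2 × (1/2)³ = 25%.

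**The case against.** **The pharmacology comes from outside.** Section 2.2 mentions no drug, and its remark on coagulation factors is limited to normal conditions. This stands in part. The class name supports the direction of the effect. It does not show that R_O carries no information in users, nor that the cheese would disturb anticoagulation at the amounts eaten. Neither is claimed here.

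**The amount of K2 cannot be worked out.** A reader might take Table I (3 + 13 + 75 = 91 µg per 100 g) and the 57 g and 65 g in section 1.5 and infer an added 52 to 59 µg of K2 a day. The documents do not support that. Section 1.5 gives those doses for menopausal age, and section 6.3.1 gives 57 g for fertile women. The doses for post-menopausal women and older men are placeholders. Section 6.2.1 also asks participants to replace their usual cheese, so the net change is smaller than the gross content for anyone who already eats cheese.

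**The shift in arm means is easy to overstate.** A reader might infer that one user lying 3 SD from the rest moves a mean of 30 by 3/30 = 0.1 SD, and three users by 0.3 SD. That applies to unadjusted means. Section 11.2 plans ANCOVA with a baseline covariate, which would absorb much of a stable difference. The 3 SD is itself an assumption.

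**The main variable is untouched.** BMD is the main response and carries the sample size. Nothing in the argument shows an effect on it. This stands.

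**There are other safeguards.** Section X lets the investigator discontinue a patient in the patient's best interests. That acts after entry and does not settle eligibility. The sentence in 8.1 reports what the authors know about adverse events and is not contradicted by the protocol. It is incomplete beside section 2.2, not wrong.

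**Conclusion.** The point holds as a gap in eligibility. Section 3.2.2 is complete as shown and admits users of vitamin K antagonists, and no other section restricts them. Eligibility is a matter for the protocol and cannot be left to an analysis plan.

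The statistical consequence is confined to cOC, ucOC and R_O. In users these would be harder to interpret, and in arms of about 30 they would add noise or chance imbalance. The size is unknown. Under the assumed prevalences, anything from no user to a handful is plausible. Even under the pessimistic assumption of complete non-response, one user in the Jarlsberg arm costs about two percentage points of power (93.4% to 91.3%), and three cost about eight (93.4% to 85.8%).

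A reader might go further and infer that the osteocalcin comparison is biased, that the BMD result is compromised, or that harm to patients has been shown. The documents support none of these. What remains is a foreseeable question about coagulation that the protocol raises in 2.2 and does not take up in 8.1, and an inexpensive improvement to the osteocalcin outcomes.

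**What to change.** - In section 3.2.2, add current treatment with a vitamin K antagonist to the drug-related exclusions, and add a matching item to the screening CRF.
- In section 8.1, address the coagulation pathway described in 2.2, so that the risk statement and the rationale agree.
- If such a drug is started during the study, identify it from the concomitant-medication record and keep the patient's values in the ITT analysis named in section 10.2. Examine the influence of those values in a sensitivity analysis only. Removing them from the main osteocalcin analysis would be an exclusion after randomisation and would conflict with ITT.

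This concerns entry to the trial and the analysis. Any rule on clinical management is for the sponsor and the investigators.

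The cost is one line in the protocol, one CRF item and a short addition to 8.1. The downside is the loss of a few otherwise eligible patients and slightly narrower generalisability.

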#### 3.3: Recruitment of patients

Participants are recruited by reading an advertisement at the medical centre. If they are interested, they contact the responsible doctor by e-mail; [[contact]](mailto:[contact]). Upon enquiry, this sends out current "Information for study participants" to the respective recruits. If, after reading this information, the person is interested and wants to participate, he/she will receive a time for the DXA measurement. If the results of this turn out to fall within the inclusion criteria, the participants make an appointment with one of the study doctors.

The recruitment letter is sent to the municipal superintendent in Lillestrøm municipality for distribution to the various doctors in the municipality. These can then look up the notice at their respective medical centres. Informed consent form must be obtained by medical

responsible physician in the study ([name] [name]) and not by someone with whom the patient has a treatment relationship. In case the patient wants to withdraw from the study, this can be stated to responsible physician classified as a neutral third party.

## IV: Design and randomization

### 4.1: Study design

The study is performed as an open randomized semi crossover design with two strata. Sex is used as a stratification factor (Figure 1). The two strata are chosen because of different OED of cheese for women and men. Within each stratum the participants will be allocated either to vitamin D + Calcium alone (Control) or with daily OED of Jarlsberg cheese (Jarlsberg). The two groups will run parallelly in 16 weeks and BMD recorded by DXA. Patient with T-score < -2.5 classifies as Osteoporotic patients will be withdrawn from the study. At week 16, the patients in the control-group will be switched to additional daily OED of Jarlsberg cheese for 32 weeks. The patients randomised to Jarlsberg will continue with the same treatment for additionally 16 weeks.

[figure not shown]

Figure 2: Study design with time schedule and variables to be recorded. Measurements given in red (x) is related only to the patients initially randomised to only vitamin D + Ca (control).

### 4.3: Identification of subjects

All the participants will be given one study identification number of four digits constructed as follows:

- Digit 1: Indicate the investigator (01, 02, 03 up to 10)
- Digit 2: Indicate the sex study arm (1=female, 2=male)
- Digit 3&4: Indicate the number consecutively within each sex arm (01,02,03 etc.)

## V: Evaluation

### 5.1: Bone mineral density (BMD)

DXA will be used as a surrogate measurement of BMD at baseline and every 16 weeks. BMD will be given in  $\text{gram}/\text{cm}^2$  and use for estimating changes in total BMD, BMD L1-L4 and left and right neck of hip. The participants will be weighed in their underwear, and height will be measured with a fixed stadiometer. A dual energy X-ray absorptiometry performing the three-site scan i) lumbar area [L2-L4], ii) femoral neck, trochanter, and shaft [proximal femur], and iii) whole body compares the bone density with the bone density expected for a healthy adult of the same age, gender, and ethnicity as the patient. The difference is calculated as a standard deviation (SD) score. The difference between the patient measurement and that of a young healthy adult is known as a T score. The T scores classifies as follows:

- above -1 SD is normal
- between -1 and -2.5 SD is defined as mildly reduced bone mineral density (BMD) compared with peak bone mass (PBM)
- below -2.5 SD is defined as osteoporosis

### 5.2: Osteocalcin and Bone turnover markers (BTM)

Blood samples for measurements of Osteocalcin, Procollagen (PINP), Collagen (CTX1), Bone specific Alkaline Phosphatase (BALP), Parathyroid hormone (PTH) will be taken at baseline and every 8 weeks. Osteocalcin will be recorded as serum Osteocalcin (tOC), carboxylated Osteocalcin (cOC), under carboxylated Osteocalcin (ucOC) and Osteocalcin ratio  $R_0 = [\text{cOC}/\text{ucOC}]$ .

### 5.3: Vitamin K

Blood samples for measurement of vitamin K will be taken at baseline and every 16 weeks. This includes vitamin K1 and the different vitamers MK -7, -8, -9 and -9(4H).

### 5.4: Laboratory variables

Blood samples for measurements of haematological and clinical biochemical variables will be taken at baseline and every 16 weeks. The required variables to be measured are listed below.

#### 5.4.1: Clinical chemistry

The following variables will be measured in serum:

- Alkaline phosphatase (ALP)
- Creatinine
- Albumin
- Urea
- ALAT
- Natrium
- Calcium
- Magnesium
- Phosphate
- Vitamin D
- HbA1C
- Total Cholesterol

HDL cholesterol  
LDL cholesterol

#### 5.4.2: Haematology

The following haematological variables will be measured:

Haemoglobin (Hgb)  
Erythrocytes  
Ferritin  
Thrombocytes  
Leucocytes

#### 5.4.2: Interleukins and Cytokines

Blood samples for measurements Interleukins (IL) and Cytokines will be taken at baseline and the last visit in the study. The chosen interleukins are IL-1 $\beta$ , IL-6, IL8, IL10 and the cytokine TNF- $\alpha$ , NF- $\kappa$  $\beta$  (RANK-L), OPG and TGF- $\beta$ .

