### 1.8.2 Clinical part

The patients will be allocated (1:1) to vitamin D + Ca-tablets  $\pm$  Jarlsberg cheese. All the participants will get new delivery of vitamin D and Ca-tablets every four weeks. The patients allocated to Jarlsberg will additionally receive Jarlsberg cheese. The patients will receive a compliance & activity form and asked to fill in every day. All the patients meet for new visits at week 4, week 16, and week 32. Patients allocated to only vitamin D + Ca tablets at baseline well additionally meet for visits at week 20 and week 48. At all these visits blood samples for

measurement of Osteocalcin, CTX-1, PINP, BALP and PTH will be drawn fasting in the morning, and concomitant medication and treatment compliance recorded. The main visits will be performed every 16 weeks. New DXA screening will be performed. Patients obtaining a BMD T-score  $\leq -2.5$  will discontinue the study and switched to antiresorptive treatment plus daily OED of Jarlsberg cheese. The daily food intake during four consecutively days will be recorded on the Diet-App. Blood samples for measurements of Osteocalcin, CTX-1, PINP, BALB and PTH will be drawn fastening in the morning at every visits. Furthermore, blood samples for measuring and biochemical variables, HbA1C and Lipids, will be recorded. The CTCAE will be recorded as well. The visit at Week 32 and Week 48 will be the last observation in the study for the patients initially allocated to Jarlsberg and controls, respectively. In addition to the mentioned variables blood samples for measurement of Interleukins and Cytokines will be performed. All the patients completed the study will be offered to continue the daily intake of Jarlsberg cheese. These patients will be followed up one year after the last visit with a new DXA and a blood sampling for measurements of the Osteocalcin level and the bone markers PINP, CTX and BALP.

**1.9: Sample size:** With a significance level of 5%, a power of 90% and a Clinically Relevant Difference (CRD) of one time the Standard Deviation in change of BMD, at least 24 patients in each group must finalize the study. With an expected drop-out rate of 25%, 30 patients in each group must be included.

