## 1.11: Flow chart

ITEMS	Screening & Baseline	Weeks					Follow-Up +1 Year
		Comparison 4	16(0)	20 (4)	Switch 32(16)	48(32)	
Inclusion and Exclusion criteria	x						
Oral & written informed consent	x						
Patient factors	x						
History of disease	x						
Diet registration	x		x		x	x	
Physical exam.	x		x		x	x	x
DXA-screening	x		x		x	x	x
Concomitant medication	x	x	x	x	x	x	x
Treatment compliance 		x	x	x	x	x	x
Blood sampling							
- Total Osteocalcin (tOC)	x	x	x	x	x	x	x
- Carboxylated Osteocalcin (cOC)	x	x	x	x	x	x	x
- Under carbox. Osteocalcin (ucOC)	x	x	x	x	x	x	x
- Collagen1 (CTX-1)	x	x	x	x	x	x	x
- Procollagen 1 (PINP)	x	x	x	x	x	x	x
- Bone specific ALP	x	x	x	x	x	x	x
- Parathyroid hormone (PTH)	x	x	x	x	x	x	x
- Vitamin K 1	x		x		x	x	
- MK-7	x		x		x	x	
- MK-8	x		x		x	x	
- MK-9	x		x		x	x	
- MK-9(4H)	x		x		x	x	
- Vitamin D	x		x		x	x	x
- Haemoglobin	x						
- Ferritin	x						
- Creatinine	x		x		x	x	
- HbA 1c	x		x		x	x	x
- Ca, Mg, Albumin	x		x		x	x	x
- Urea, Phosphate	x		x		x	x	x
- LDL-cholesterol	x		x		x	x	x
- HDL-cholesterol	x		x		x	x	x
- Interleukins /cytokines	x				x	x	
- TSH & FT4	x				x	x	
Adverse Events [CTCAE]	x	x	x	x	x	x	
End of treatment					x	x	

**Red numbers** indicate only the visits after switching to Jarlsberg in the control group.

 Treatment compliance will be performed every four weeks.

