#### 6.2.2: Comparative phase

All the participants meet for clinical investigations at week 4 and week 16 in the comparative phase of the study. At week 4, blood samples will be taken for measurements of Osteocalcin and the BTMs. Additionally, concomitant medication, adverse events (AE) and treatment compliance will be recorded. Cheese and vitamin D + Ca for the next 4 weeks will be delivered. A new delivery will be handed over by a representative from the Meddoc team at week 8 and week 12 in the study. The last clinical investigation in this comparative phase will be performed at week 16. The physical examination will be equal with the one performed in the screening phase. The patients must perform a new diet registration during the following 4 days and undergo the second DXA investigation for measurements of BMD. Additionally, the patients will record their change in concomitant medication. Blood samples will be collected for measurements of Osteocalcin, vitamin K2, BTMs, HbA1C, Lipids and other hematological and biochemical variables. Patients with a T-score < -2.5 based on the DXA investigation will be classified as Osteoporotic and withdrawn from the study. If possible and

in accordance with the responsible investigator, the patient will be given Antiresorptive treatment in addition to OED of Jarlsberg cheese and vitamin D + Ca.

The patients randomized to only vitamin D + Ca (Controls) at baseline will now receive OED of Jarlsberg cheese equal with the other patients and continue in the follow-up phase of the study. Cheese for the next 4 weeks will be delivered together with compliance & activity form.

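### Interleukins and cytokines are sampled only at baseline and at each arm's last visit, when both arms have had 32 weeks of cheese, so these eight analytes have no randomised cheese versus no-cheese comparison

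*Protocol*

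**What the plan says.** **Sampling times.** Section 5.4.2 (Interleukins and Cytokines) lists four interleukins and four cytokines, for which blood "will be taken at baseline and the last visit in the study". Section 1.7 (Main variables) agrees: they "will be measured initially and at the last visit in the study". Section 1.8.2, having set the final visits at week 32 for the Jarlsberg arm and week 48 for controls, adds: "In addition to the mentioned variables blood samples for measurement of Interleukins and Cytokines will be performed". In the flow chart (1.11) the row "Interleukins /cytokines" is marked at baseline, week 32(16) and week 48(32), and is blank at weeks 4, 16 and 20.

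**Week 16.** Section 6.2.2 gives the blood list for the visit that closes the comparative phase: "Blood samples will be collected for measurements of Osteocalcin, vitamin K2, BTMs, HbA1C, Lipids and other hematological and biochemical variables". Interleukins and cytokines are not on it. They are on the week-32 list in 6.2.3.

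**Treatment periods.** Section 4.1 states that "The two groups will run parallelly in 16 weeks" and then: "At week 16, the patients in the control-group will be switched to additional daily OED of Jarlsberg cheese for 32 weeks". The Jarlsberg arm continues for 16 more weeks. Section 6.2.4 confirms week 32 and week 48 as the end of study. Under 6.3.1 every patient takes vitamin D and calcium throughout.

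**Analysis.** Section 11.2 plans ANCOVA with a baseline covariate for comparing groups on continuous variables and makes no exception for this panel.

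**The concern.** The comparative aim (1.3 and 2.4) is vitamin D + Ca with cheese against vitamin D + Ca without it. That contrast exists only until controls switch at week 16. A variable not measured between baseline and the switch cannot be compared on those terms, and no later analysis plan can recover a value that was never drawn.

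What is at stake is the use of the panel. Under 11.2 the cytokines would go through the same between-group ANCOVA as everything else. A null result could be read as showing that cheese has no effect, although both arms have had the same amount. A difference could be credited to cheese when it reflects elapsed time or a longer course of supplements.

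**Working it through.** **Inputs**
- Cheese starts at week 0 in the Jarlsberg arm and at week 16 in the control arm (4.1).
- The last visit is week 32 (Jarlsberg) or week 48 (control) (6.2.4).
- Vitamin D + Ca runs from baseline to the end of study in both arms (6.3.1).
- Cytokines are sampled at baseline and the last visit (1.7, 1.8.2, 5.4.2).

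**Formula.** Weeks of cheese at a visit = visit week - week cheese starts, with a minimum of 0.

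**The protocol's own figure.** Controls: 48 - 16 = 32 weeks, which reproduces the 32 weeks stated in 4.1. Jarlsberg: 32 - 0 = 32 weeks, which agrees with 16 + 16 in 4.1.

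**All visits**

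| Visit | Jarlsberg: weeks of cheese | Control: weeks of cheese | Cytokines sampled (text) |
|---|---|---|---|
| Baseline | 0 | 0 | both arms |
| Week 4 | 4 | 0 | no |
| Week 16 | 16 | 0 | no |
| Week 20 | 20 (no visit) | 4 | no |
| Week 32 | 32 | 16 | Jarlsberg only |
| Week 48 | finished | 32 | control only |

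Controls are cheese-free after baseline only at weeks 4 and 16, and cytokines are sampled at neither.

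**What the last-visit contrast contains**
- Cheese: 32 v 32 weeks, a difference of 0.
- Study week: 32 v 48, a difference of 16.
- Vitamin D + Ca: 32 v 48 weeks, a difference of 16.

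The arms are therefore equal on the factor of interest and unequal on two others.

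**With the second sample at week 16.** Cheese is 16 v 0 weeks, study week 16 v 16, and vitamin D + Ca 16 v 16 weeks. Only cheese differs.

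**Panels.** With about 30 patients per arm (1.9, 11.3), the present schedule is 2 x 30 x 2 = 120 panels of eight analytes. Moving the second sample leaves 120. Adding week 16 and keeping the last visit adds 2 x 30 = 60.

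**The case against.** The best defence is one of rank. Cytokines are not named in either list of aims, and section 1.7 places them outside the main and second main variables. No cytokine hypothesis or power claim is made, and the only link to a between-group test is the general ANCOVA sentence in 11.2. Measuring an exploratory panel at start and end only is an ordinary way to save resources, and it yields a value at full exposure in both arms. This stands, and it is why the point is minor.

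Three stronger readings are tempting, and the protocol supports none of them.

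- **That there is no randomised comparison of any kind.** A reader might infer this, but the arms remain randomised at the last visit. What is compared there is immediate cheese against 16 weeks of supplements followed by cheese. That is a comparison of sequences. It is not one of cheese with no cheese.
- **That the expected difference is zero, so power equals the 5% significance level.** This would hold only if study week and supplement duration had no influence, and both differ by 16 weeks. The contrast is confounded, and no power figure should be attached to it.
- **That controls also have a week-32 sample that could be dropped to pay for a week-16 one.** The mark under week 32(16) in the flow chart invites this. But the chart uses colour to separate control-only visits, and the colour is lost in the text at hand. Sections 1.7 and 5.4.2 say last visit only, and 6.2.3 equates the controls' week-32 visit with the Jarlsberg week-16 visit, which has no cytokines. Even if that sample were taken, it would compare 32 with 16 weeks of cheese, still without a cheese-free group.

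**Conclusion.** The point holds in a limited form. As scheduled, the eight interleukins and cytokines cannot be used to compare cheese with no cheese between randomised arms. The last-visit comparison does not estimate the cheese effect, and within-arm change from baseline cannot be separated from time or from the supplements that everyone takes.

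The conclusion rests on the visit schedule alone and needs no assumption about effect size or variance. It does assume that the text in 1.7, 1.8.2 and 5.4.2 governs where the flow chart is ambiguous, but the other reading of the chart would not supply a cheese-free control either. The week-16 comparisons of BMD, osteocalcin and bone markers are untouched. This is a minor but cheap improvement and does not affect the trial's main result.

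**What to change.** Move the second cytokine sample to week 16 in both arms, drawn before controls take their first cheese. Fasting blood is already taken from everyone at that visit (1.8.2, 6.2.2), so no new visit or venepuncture is needed.

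Amend 1.7, 1.8.2, the flow chart in 1.11, 5.4.2, 6.2.2 and 6.2.3 together. Section 6.2.3 needs care: it equates the controls' week-32 visit with the Jarlsberg week-16 visit, so an unqualified change at week 16 would also add a control sample at week 32.

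**Cost.** The number of assays is unchanged if the sample is moved, but the value after 32 weeks of cheese is given up in both arms. If that value is wanted too, keep the last-visit sample and budget for one further panel per patient, up to about 60. If the sponsor prefers the present schedule, the protocol should say that the panel is descriptive within each arm and take it out of the between-group ANCOVA in 11.2.
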